Official Study Title: Remineralization of Molar Incisor Hypomineralization (MIH) with a Hydroxyapatite Toothpaste – an *in situ* study

NCT number: NCT 05485662

IRB Approval Date: 01/05/2022

Unique Protocol ID: HSC20210570H

**Remineralization of Molar Incisor Hypomineralization (MIH) with a Hydroxyapatite Toothpaste –
an *in situ* study**

Institution:

University of Texas Health San Antonio

[name]

Investigator and Affiliations:

[name], BDS, MS, MFDS RCPS (Glasg), PhD, FADI

Professor and Director of Cariology

Department of Comprehensive Dentistry

University of Texas Health San Antonio

[name]

Representatives of Sponsoring Company:

[name] and [name]

Senior Scientists Oral Care

DR. KURT WOLFF GMBH & CO. KG

[name]

[name]

Germany

A. Null Hypothesis

1. Hypomineralized enamel treated with hydroxyapatite toothpaste would not regain up to 20% mineral density relative to healthy enamel.
2. The effectiveness of hydroxyapatite toothpaste in remineralizing MIH would not be significantly different from that of 1450 ppm fluoride toothpaste.

B. Specific Aims

The objective of this *in situ* clinical study is to determine whether a toothpaste formulation containing hydroxyapatite is effective in promoting remineralization of molar incisor hypomineralization (MIH), in comparison to a toothpaste formulation containing 1450 ppm fluoride. Effectiveness will be declared if the MIH lesion regain up to 20% mineral density relative to healthy enamel.

C. Significance / Background

MIH is a qualitative enamel defect observed on at least one first permanent molar (FPM) with or without affecting permanent maxillary incisors¹. Clinically, it's diagnosed when a FPM presents with a demarcated opacity, larger than 1 mm, varying in color from white to yellow and even brown^{2,3}. Additionally, post-eruptive enamel breakdown, atypically sized, shaped, and extended restorations, or a history of extraction of FPMs in an otherwise sound dentition, are also diagnostic criteria of MIH. The location, asymmetry and varying severity of the defects, distinguishes them from other enamel mineralization defects such as fluorosis⁴. The severity of the affection can be divided into 2 categories, mild and moderate/severe. These categories are differentiated clinically by the presence or absence of enamel breakdown, the degree of hypersensitivity and the esthetic concerns³. It is also correlated with reduced levels of mineral density (MD) of the affected enamel to 2.24 g/m³ in mild cases and 1.93 g/m³ in moderate/severe cases in comparison to a 2.51 g/m³ average MD of normal enamel⁵.

Hypomineralization can affect both primary and permanent teeth, but the molar-incisor model is the most common with a reported prevalence between 10% to 20%^{6,7}. As for their etiology, MIH defects can result from genetic or systemic environmental factors. Perinatal and postnatal factors appear to be the most strongly associated with its occurrence⁸. In fact, premature birth and associated complications, hypoxia, dioxin exposure and other childhood illnesses such as ear or respiratory infections and antibiotic use are implicated in an increased incidence of MIH. If these conditions develop in the early childhood, up to age 3, when the crowns of the FPMs and incisors are

undergoing mineralization, they predispose the child to MIH^{3,9}. Consequently, the time of onset, span and severity of the conditions dictate the pattern and intensity of the lesions.

Management of MIH defects is complicated by the penetration of bacteria through the often-exposed dentinal tubules¹⁰. This process causes subclinical inflammation of the pulp and hypersensitivity that lead to a higher anesthetic threshold and negligence of oral hygiene by the child subsequently increasing the need for dental treatment¹¹. Additionally, esthetic and functional concerns are frequent in these patients and are associated with a lower oral health related quality of life¹². The treatment of teeth with hypomineralization defects is twofold, preventive and/or interventional. Therapeutic interventions must take place when the teeth display severe defects, enamel breakdown, decay or signs of pulpal inflammation/infection¹³. This approach includes restoration with glass ionomer, composite resin or preformed metallic crowns for posterior teeth and micro-abrasion with resin infiltration and composite restoration for anterior teeth and extraction with space management for non-restorable teeth^{3,14}. However, when MIH diagnosis is established early, the prevention of the progression of the defect is recommended by using sealants and promoting remineralization. In fact, increasing the mineral content of the enamel to a threshold close to the norm can improve its physical properties, hence improving the esthetic and functional outcomes. Several techniques pertaining to remineralization of MIH lesions have been described in the literature including the use of low-level laser therapy or the application of pastes and varnishes containing arginine, fluoride (with or without tricalcium phosphate), casein phosphopeptide-amorphous calcium phosphate (CPP-ACP) or casein phosphopeptide-amorphous calcium fluoride phosphate (CPP-ACFP)¹³. Toothpastes containing nanohydroxyapatite (HAP) were shown to have comparable effects to fluoride toothpastes in terms of remineralization of incipient carious lesions and prevention of decay, while excluding the risk of fluorosis¹⁵. The synthesized particles of HAP are structurally similar to the crystals found in enamel and dentin, have analogous properties and can readily penetrate enamel surface¹⁶. However, their use as a mean of increasing mineral density in MIH defects has not been investigated. Thus, the objective of this study is to determine the effectiveness of a toothpaste containing HAP in promoting remineralization of teeth with MIH defects.

D. Experimental Design

Production of Samples

30 freshly extracted permanent teeth with MIH will be collected from the pediatric clinics of the University of Texas Health San Antonio (UTHSA). These teeth were extracted as part of the patient's standard of care and

donation will be done based on the patients willingness. If the patient wishes to donate the teeth, they will be placed in a container within the pediatric dental clinics and will be donated without identifiable information attached to them. The teeth will be cleaned of debris/stains and examined with a transilluminator. Teeth with MIH but free of caries or other malformations will be selected and cleaned with pumice to remove the pellicle. Using a water-cooled diamond wire saw, 3 blocks, two from MIH affected area and one from a healthy area will be produced from each tooth, with each block measuring approximately 2 mm length x 2 mm width x 1 mm thickness. The cut will take place so that the different layers from the outer surface to the inner surface present in each block are: outer enamel surface, enamel, dentino-enamel junction (DEJ) and dentin.

Measurement of baseline mineral density of the tooth blocks

Micro computed X-ray tomography (μ -CT) is a high resolution, non-destructive radiographic method of analysis that generates qualitative images and quantitative analysis of the mineral density (MD) in tooth samples. For this reason, images will be collected from the samples to measure the mineral density of the MIH enamel lesions before (MD_b) and after (MD_t) remineralization treatment as well as the mineral density (MDs) of healthy enamel samples. The μ -CT scanning and analysis procedure will be performed as described in our previous publications.¹⁷

Study Population/Participants

Fifteen subjects (8 females, 7 males) will be recruited into the study. The subjects to be included should be 18 to 60 years old in good general health with no known history of allergy to personal care/consumer products. They must have a minimum of 20 natural uncrowned teeth (excluding third molars), no active unrestored cavities and a normal salivary flow rate (stimulated and unstimulated flow of ≥ 0.7 ml/min and ≥ 0.2 ml/min respectively) ascertained from a preliminary sialometry test. They also should give written informed consent, be available throughout entire study, and be willing to wear intra-oral appliance 24 hours per day and use only assigned products for oral hygiene throughout the duration of the study.

The exclusion criteria are having advanced periodontal disease, a medical condition that requires premedication prior to dental visits/procedures, an impaired salivary function, wearing an orthodontic retainer(s), not having enough teeth to secure the oral appliance, having diseases of the soft or hard oral tissues, using drugs that can affect salivary flow, using antibiotics one month prior to or during this study, participating in another clinical study one week prior to the start of the washout period or during this study period, using tobacco products, having an allergic

history to common toothpaste ingredients, and having a compromised immune system (HIV, AIDS, immuno-suppressive drug therapy) as determined by review of medical history

Recruitment of Study Subjects

This is a double-blind, randomized, crossover, single center, controlled clinical trial. The study will be blinded to both the study team and the subjects. Recruitment of potential subjects will be from the local San Antonio area. The subjects will be identified with code numbers (CP01 to CP15). The approval of the UTHSA IRB will be obtained. This study will be conducted in compliance with International Conference on Harmonization (ICH) Good Clinical Practice Guidelines. At the screening visit, each subject will complete a medical / dental history and read and sign an informed consent form. Following consent, a visual oral health exam will be performed by a licensed dentist. Subjects will be enrolled based on all the inclusion and exclusion criteria and other screening evaluations such as preliminary sialometry, and then randomly assigned to one of two treatment sequences.

Construction of the *in-situ* appliance

The 3 blocks from each tooth will be used, as follows: two blocks with MIH lesions will be used for remineralization assessment and one healthy tooth block will serve as control for the MD of healthy enamel. The MIH-bearing blocks will be covered with polyester gauze (Bard Peripheral Vascular, Inc., USA), which will facilitate plaque retention on the surface of the tooth blocks on intra-oral exposure. Following recruitment, an impression of the subject's lower dentition will be taken using an alginate impression material. A dental technician will fabricate a lower removable intra-oral appliance. Each of the MIH-lesion-bearing blocks will be mounted on each side within the acrylic portion of the removable appliance, using Intermediate Restorative Material (IRM) cement (fluoride-free). All appliances are sterilized with ethylene oxide prior to delivery to the subject.

Test Product Description and Labeling

The toothpastes to be used for treatments are 10% HAP toothpaste, 1450 ppm NaF fluoride toothpaste, and non-fluoride toothpaste (washout). The 2 test products will be coded by the manufacturing/packaging company, who will retain the code until the completion of the study and data interpretation. The experiment will consist of two distinct treatment phases, Phase 1 and Phase 2, during which subjects will be exposed to one of the 2 products in a randomized crossover design, with each phase lasting for 2 weeks.

Study Procedure and Patient Instructions

Prior to each 2-week treatment phase, subjects will complete a 1-week washout period. This period allows for attenuation of any residual effect of the subject's previously used toothpaste. During this period, no appliance will be worn, and subjects will be using only the provided washout toothpaste and a soft-bristled toothbrush twice daily. Following the washout period, the intra-oral appliance will be fitted to each subject by a qualified dentist. Immediately after fitting of the first appliance (on day 1 of the first treatment phase), each subject will receive a soft bristled manual toothbrush for use throughout the duration of the study and a toothpaste according to the treatment phase. They will make the first use of the test product under the supervision of the study coordinator. For the remainder of the study, subjects will complete the procedure at home and as instructed.

The subjects will be instructed to brush their teeth with the appliance in the mouth, two times daily, for 3 minutes on each brushing episode, in the morning after breakfast and last thing before bed, then rinsing with 10 ml of water. In dispensing the toothpaste onto the toothbrush, the subjects should fill the toothbrush surface from end to end but no more than one ribbon of toothpaste. The subjects will be advised not to brush directly on the blocks but rather to brush around the blocks to prevent disruption of the plaque. Subjects should neither eat nor take any drink for at least 30 minutes after brushing, they will be also instructed to remove the appliance while eating. A timer and measuring cup will be provided to each subject. To monitor product usage and compliance, a diary will be provided to each subject and checked at every visit, to record the number of tooth-brushings performed each day and the time it was done. Further, subjects will be instructed to return the remaining washout or test toothpaste after each treatment phase. The weight of toothpaste will be measured before and after each treatment phase. Over the study period, all subjects are to maintain their normal dietary habits.

On day 15, the subject, without using the product that morning, will arrive at the clinic, and the tooth block will be harvested and sent to the laboratory for μ CT analysis. Then the subject will be given washout toothpaste and a soft-bristle toothbrush to undergo another 7-day washout period without an appliance. After completion of the second washout period, subjects will return to the clinic, and the appliance, with another MIH-bearing tooth blocks mounted, will be fitted to the subject for the phase 2 treatment period. This procedure will then be repeated until the 2-week treatment phase is completed, and each subject has gone through the two arms of the study.

Upon completion of the treatment phases, the post-remineralization mineral density (MDt) of all the MIH-lesion-bearing blocks exposed intra-orally for remineralization will be assessed with μ CT. For the lesion-bearing blocks,

this process will yield the following information: the pre-test (MD_b) and post-test (MD_t) mineral density of the lesions and their associated images, while for the healthy tooth blocks, the MDs and the μ CT images.

At every visit, the dental examiner will visually examine the soft and hard tissues of the oral cavity and peri-oral area using a dental light and dental mirror. Additionally, subjects will be asked about and examined for any adverse events. Subjects may call and request a visit for any concern of potential adverse event.

Data Handling

Using the μ CT images, the pattern and the extent of remineralization produced within each lesion by each treatment product will be examined and described. This will be clearly shown by comparing the pre- and post-test images side-by-side. For all calculations, the absolute MD will be measured and used. For the remineralization blocks, the values of the MD_b and MD_t for each test product will be compared using paired t-test to determine any significant change (remineralization) made by the test product (intra-group comparison). However, to make comparisons between the two products (intergroup comparison), percentage change in MD calculated relative to the control will be determined for each test product as such: % Change in MD (% Δ MD) = [(MD_b – MD_t)/MD_b] x 100

The percentage MD recovery following remineralization will be calculated as follows:

% MD recovery (%MDR) = [(B-T)/(B-S)] x 100, with S = mean MDs of healthy enamel blocks, B = mean MD_b of MIH enamel blocks before remineralization, and T = mean MD_t of MIH enamel blocks after intra-oral exposure.

Sample Size Calculation

The power analysis and sample size calculation were performed using nQuery Advisor software (Statistical Solutions, Cork, Ireland). The sample size for this study is based on the primary efficacy parameter, % MDR following 2 weeks of treatment. A sufficient number of subjects will be screened to randomize approximately 15 subjects with the intention that approximately 15 subjects complete all study treatments and be evaluable for the efficacy analysis. With these conditions met, the study will have 80% power at the 5% significance level, using two-sided testing, to detect a mean treatment difference in %MDR of approximately 8.1% assuming a within subject standard deviation of approximately 12.6%. In the absence of available 2 week data from previous mineral density studies, the within subject standard deviation has been estimated using 14-day post-treatment data from a previous results obtained by this group in a demineralization and remineralization study using HAP toothpaste¹⁵. In that study the mean % change in mineral loss was equal to 30.3 with a standard deviation equal to 16.3.

Statistical Analysis

After assumptions of normality and homogeneity of variances have been verified by normal probability plots, comparisons of the mean values of MD, %ΔMD and %MDR between the two treatment groups as well as the intra-group comparisons will be performed using the paired Student's t-test (STATA version 10.0, StataCorp LP, USA) at a significance level of 5%. The primary endpoints of the present study are expected to be enhanced remineralization of MIH lesion.

E. References

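### Null hypothesis 1 and the effectiveness rule turn on a 20% regain, but no planned analysis tests against 20%.

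*Combined protocol and SAP*

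**What the plan says.** The 20% figure appears in two places. Section A, null hypothesis 1: "Hypomineralized enamel treated with hydroxyapatite toothpaste would not regain up to 20% mineral density relative to healthy enamel". Section B gives the matching rule: "Effectiveness will be declared if the MIH lesion regain up to 20% mineral density relative to healthy enamel". It is not mentioned again.

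Under Data Handling, the within-product analysis is that "the values of the MD_b and MD_t for each test product will be compared using paired t-test to determine any significant change (remineralization"). For comparing products, two percentages are defined:

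- %ΔMD is introduced by "percentage change in MD calculated relative to the control will be determined for each test product", but its formula divides by the baseline value MD_b and contains no healthy-enamel term.
- %MDR is 100 × (B−T)/(B−S), with "S = mean MDs of healthy enamel blocks, B = mean MD_b of MIH enamel blocks before remineralization" and T the corresponding mean after exposure.

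Statistical Analysis applies the paired t-test to MD, %ΔMD and %MDR between products, and to the within-product comparisons. On sample size: "The sample size for this study is based on the primary efficacy parameter, % MDR following 2 weeks of treatment". The stated power is to "detect a mean treatment difference in %MDR of approximately 8.1% assuming a within subject standard deviation of approximately 12.6" percent, which is a between-product contrast.

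**The concern.** A trial that declares effectiveness on a numerical threshold needs an analysis that can accept or reject that threshold. Here the only within-product test asks whether mineral density changed at all, which is a much weaker question than whether a fifth of the deficit was regained. The between-product tests ask something else again: both products could recover 5%, or both 40%, with no difference between them.

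At stake is the first of the two stated hypotheses. As planned, it has no test, no error rate and no stated power. The easy mistake at reporting is to present a significant before-after test as support for hypothesis 1 when it does not address the 20%. Any comparison of %MDR with 20 would have its criterion and its averaging chosen after the data are in.

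**Working it through.** **The plan's own figure.** The protocol gives no power, sample size or error rate for the 20% threshold, so there is nothing to reproduce on this point. The stated 80% power concerns the 8.1-point difference between products. (With n = 15, two-sided 5% and 12.6 taken as the SD of the paired difference, I get 63.9% for that contrast. That is a separate matter and nothing below depends on it.)

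**Step 1: what each planned test has as its null.**

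| Planned test | Null value | Addresses 20%? |
|---|---|---|
| MD_b against MD_t, within product | change = 0 | no |
| MD, %ΔMD, %MDR, between products | difference = 0 | no |

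**Step 2: which scale the 20% belongs to.** Section C gives average densities of 2.51 (normal), 2.24 (mild) and 1.93 (moderate/severe). The deficits are 2.51 − 2.24 = 0.27 and 2.51 − 1.93 = 0.58.

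| Reading of 20% | Gain, mild | Gain, moderate/severe |
|---|---|---|
| %MDR: 0.20 × deficit | 0.054 | 0.116 |
| %ΔMD: 0.20 × MD_b | 0.448 (166% of deficit) | 0.386 (67%) |
| 0.20 × healthy density | 0.502 (186%) | 0.502 (87%) |

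The last two readings would take an average mild lesion above normal enamel. %MDR is the only defined percentage that uses healthy density, and it is the primary efficacy parameter. It is the evident scale.

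**Step 3: how far the zero-change test is from the 20% question.** Inputs: n = 15 (Sample Size Calculation) and t(0.975, 14 df) = 2.145. The between-subject SD of %MDR is not given anywhere. I assume 12.6 to 16.3. The first is the protocol's within-subject SD. The second comes from the earlier study: "In that study the mean % change in mineral loss was equal to 30.3 with a standard deviation equal to 16.3". Neither is established for this use, and they are not bounds. If all deficits are equal, testing MD_b against MD_t is the same as testing mean %MDR against 0.

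- SE = SD/√15 = 3.253 (SD 12.6) or 4.209 (SD 16.3).
- Significant against 0 from an observed mean of 2.145 × SE = 6.98 or 9.03.
- Lower 95% limit above 20 needs an observed mean of 20 + 2.145 × SE = 26.98 or 29.03.
- At a true mean of 15%, below the threshold, the zero-change test is significant with probability 0.990 or 0.912 (noncentral t).

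Over a wider SD range of 8 to 25, the zero-change cut-off runs from 4.4 to 13.8%, and the cut-off for a lower limit above 20 from 24.4 to 33.8%. With an even mix of deficits 0.27 and 0.58 (also an assumption; by simulation, SD 12.6 and 16.3), the zero-change cut-offs are 7.6 and 9.8% and the probabilities at a true 15% are 0.98 and 0.88.

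**Step 4: why one analysis must govern.** %MDR can be formed as a ratio of means or as a mean of per-subject ratios. Assume 7 mild and 8 moderate/severe subjects, each gaining 0.08. Mean deficit = (7 × 0.27 + 8 × 0.58)/15 = 0.4353, so the ratio of means is 0.08/0.4353 = 18.4%. The mean of ratios is (7 × 29.63 + 8 × 13.79)/15 = 21.2%. The two fall on opposite sides of 20. In simulation with an even mix and a true mean of 25%, the two corresponding one-sample tests reach different decisions in about 7 to 9% of trials.

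**The case against.** The best defence is that the plan can be read sensibly without amendment: compute %MDR for the hydroxyapatite product and see whether it reaches 20. Much of this stands, and it rules out several stronger criticisms that a reader might infer.

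- *That the scale is unknown.* Not supported. Section B ties the regain to healthy enamel, and Step 2 leaves %MDR as the only natural reading. What is missing is a cross-reference.
- *That the words* up to *set a ceiling.* Not supported as a serious reading, since a ceiling makes no sense as a rule for declaring effectiveness. The phrase is loose and should be replaced.
- *That %MDR cannot exist per subject.* Not supported. A within-subject SD and a paired t-test imply one value per subject and product. The gap is that B, T and S carry no subject index, and that S could be the same tooth's healthy block or a pooled mean.
- *That there is no decision rule, or that the before-after test is the rule.* Neither is supported. A verbal rule exists, and it is not the before-after test. At a true mean of exactly 20%, a point-estimate rule succeeds 50% of the time and a lower-limit rule 2.5%, but that is true of any such pair of rules and is not a defect peculiar to this plan.

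It is also fair that the magnitudes are illustrative, because the SD and the severity mix are assumed, and that a confidence-limit rule is stricter than Section B spells out. The defence does not supply the missing analysis: the comparison with 20 is nowhere written as a test, and a stated null hypothesis calls for one.

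**Conclusion.** The point holds: hypothesis 1 and the effectiveness rule depend on a threshold that no planned analysis tests. This follows from reading the sections together and does not depend on any assumed SD. The size of the gap does: under SDs of 12.6 to 16.3, n = 15 and equal deficits, the planned test becomes significant at roughly 7 to 9% observed recovery, while demonstrating more than 20% with a 95% limit needs roughly 27 to 29%. The loose wording of the threshold, the unstated link to %MDR and the missing subject index are secondary points of drafting. It should be fixed before the data are analysed; it does not undermine the design or the between-product comparison.

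**What to change.** 1. In Sections A and B, state that the 20% refers to %MDR in the hydroxyapatite phase, and word it as a minimum to be reached.
2. Index %MDR by subject and product: 100 × (T−B)/(S−B), algebraically the same as the Data Handling formula, with B and T averaged over that subject's blocks in the phase. State in advance whether S is the healthy block of the same tooth or the pooled mean; if the former, record each block's tooth of origin.
3. Name one governing analysis of hypothesis 1: a one-sample t analysis, in the hydroxyapatite phase, of the per-subject value (T−B) − 0.20 × (S−B) against 0, with its two-sided 95% CI. This keeps the ratio-of-means form and stays stable when a deficit is small. Give the one-sample t-test of per-subject %MDR against 20 as a sensitivity analysis only.
4. Reject null hypothesis 1 only if the lower 95% limit of the governing analysis exceeds its threshold (0 on that scale). Treat the MD_b versus MD_t test as evidence of any change only.
5. State the power against 20%.

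Cost: rewording, a subject-level formula and one added analysis, with no new data or subjects. The downside is power. Under the assumed SDs of 12.6 to 16.3 with equal deficits, it is about 30 to 20% at a true mean of 25% and 82 to 60% at 30%; 80% power needs a true mean of about 29.8 to 32.7%. The linear form weights subjects by deficit, so with an even mix of mild and moderate/severe deficits it drops to about 27 to 18% at 25%. A trial of this size may therefore fail to reject hypothesis 1 even when the true recovery is somewhat above 20%, and the protocol should say so.

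### The objective compares HAP with fluoride, but the effectiveness declaration rests on a 20% regain alone, so HAP could be declared effective while significantly worse than fluoride

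*Combined protocol and SAP*

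**What the plan says.** All references are to the combined protocol and SAP.

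- **Section A, Null Hypothesis** lists two hypotheses with no order between them. The first concerns one product: "Hypomineralized enamel treated with hydroxyapatite toothpaste would not regain up to 20% mineral density relative to healthy enamel". The second is comparative: the effectiveness of HAP "would not be significantly different from that of 1450 ppm fluoride toothpaste".
- **Section B, Specific Aims** asks whether HAP is effective "in comparison to a toothpaste formulation containing 1450 ppm fluoride". The next sentence is the declaration rule: "Effectiveness will be declared if the MIH lesion regain up to 20% mineral density relative to healthy enamel".
- **Section C, Significance / Background** closes by restating the aim without a comparator: "the objective of this study is to determine the effectiveness of a toothpaste containing HAP in promoting remineralization of teeth with MIH defects".
- **Section D, Data Handling** plans a before-after paired test within each product and a comparison between products.
- **Section D, Sample Size Calculation** states: "The sample size for this study is based on the primary efficacy parameter, % MDR following 2 weeks of treatment". The stated power is "to detect a mean treatment difference in %MDR of approximately 8.1" percentage points, so the sizing contrast is between products.
- **Section D, Statistical Analysis** plans paired t-tests between and within products at 5%, and ends: "The primary endpoints of the present study are expected to be enhanced remineralization of MIH lesion". That sentence names no contrast.

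**The concern.** The declaration rule sits directly under a comparative objective, yet it can be satisfied without looking at the fluoride phase. The contrast that the crossover is randomised, blinded and sized to estimate is HAP minus fluoride, and it has no stated bearing on the declaration. The two contrasts can point in opposite directions in the same data, and the plan does not say what is concluded when they do. A report could then state, in keeping with the protocol, that HAP was effective in a study whose objective was comparison with fluoride, although the paired test favoured fluoride.

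**Working it through.** **1. The plan's own figure.** Inputs from Sample Size Calculation: n = 15, difference 8.1 points, within-subject SD 12.6, two-sided 5%, power 80%. The text does not make clear whether 12.6 is the SD of the paired difference or the SD per phase, so both are shown.

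- SD of differences 12.6: SE = 12.6/√15 = 3.253, and 8.1/3.253 = 2.49. Two-sided paired-t power (14 df) is 63.9%; the normal approximation gives 70.2%.
- SD per phase 12.6: SD of differences = √2 × 12.6 = 17.8, SE = 4.601, and 8.1/4.601 = 1.76. Two-sided paired-t power is 37.5%.
- At n = 15, of the variants tried, only a one-sided 5% normal approximation with SD of differences 12.6 returns the stated figure (80.1%). That conflicts with the stated two-sided testing.

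The present point does not depend on this discrepancy, but the fix does (see below).

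**2. Can both conditions hold together?** The smallest observed difference that is significant at two-sided 5% is t(0.975, 14) × SE, with t = 2.145:

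- SD of differences 12.6: 2.145 × 3.253 = 7.0 points.
- SD of differences 17.8: 2.145 × 4.601 = 9.9 points.

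Take observed mean %MDR of 21 for HAP and 32 for fluoride. HAP passes 20. The difference is 11 points, so t = 11/3.253 = 3.38 or 11/4.601 = 2.39. Both exceed 2.145. This step assumes nothing about true means.

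**3. How often?** This step needs assumptions that the documents do not supply. Model: a subject's %MDR = product mean + subject effect + error, with error SD 12.6 per product and subject-effect SD 0, 10 or 16.3 (assumed; 16.3 is the SD quoted from the earlier study, used here only as an upper value). HAP counts as effective if its mean %MDR is at least 20, and as worse if the two-sided 5% paired t-test favours fluoride. n = 15, with at least 100,000 simulated trials per scenario.

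| Assumed true %MDR, HAP v fluoride | Probability of effective and significantly worse |
|---|---|
| 25 v 25 | about 1% |
| 25 v 30 | 11–13% |
| 25 v 33.1 (8.1-point design difference) | 27–32% |
| 25 v 35 | 40–47% |

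If 12.6 is instead the SD of the paired difference (subject-effect SD 0 or 10.3), the figures are higher: about 2% for 25 v 25, 57–62% for 25 v 33.1, and 74–80% for 25 v 35.

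**The case against.** The strongest reply is that Section A already separates the two questions. Null hypothesis 1 uses the same 20% wording and names hydroxyapatite, so the product behind the rule is identifiable. Null hypothesis 2 gives the fluoride comparison its own test. %MDR is called the primary efficacy parameter and the sample size rests on the treatment difference, so the between-product contrast is implicitly primary. An inferior HAP result would be detected and reported. A product can also reach an absolute threshold and still be less effective than an active comparator, so an absolute criterion beside a comparison is a legitimate design.

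All of this stands. A reader might infer that the plan gives no clue to its main contrast, or that the fluoride comparison has no place in it; Section A and Sample Size Calculation do not support that. What remains is narrower: a sizing basis is not a decision rule, the only declaration sentence follows the comparative objective without a fluoride term, and no sentence says how the two hypotheses combine.

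A reader might also infer that a contradictory result is likely. The documents give no expected values for the two products. Section C reports comparable effects of HAP and fluoride toothpastes, though in early caries and not in MIH. High probabilities need an assumed fluoride advantage larger than the 8.1-point design difference or the smaller reading of the SD. They also need 20% to mean mean %MDR. If it meant 20% of healthy density, the Section C figures would require a gain of 0.2 × 2.51 = 0.502 against deficits of 2.51 − 2.24 = 0.27 (mild) and 2.51 − 1.93 = 0.58 (moderate/severe). That is 186% and 87% recovery, so the rule would seldom be met and the table would not apply.

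Finally, a reader might count the before-after tests as further claims and infer an inflated error rate. No part of the plan declares effectiveness from those tests, so that does not follow.

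**Conclusion.** The point holds as a gap in the decision rule. The declaration in Section B answers null hypothesis 1 only. The comparative objective is answered by null hypothesis 2, the contrast the trial is sized on, and nothing ties that result to the declaration. The closing primary-endpoint sentence does not repair this.

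That the two results can conflict is shown by arithmetic on the plan's own n and SD, reading the 20% rule as observed mean %MDR of at least 20. How often they would conflict is not known: it is negligible if the products perform alike and substantial if fluoride leads by the design difference or more, and every true mean used is an assumption. The data would remain analysable either way. What is not fixed in advance is the headline conclusion.

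**What to change.** In Section B, and again under Statistical Analysis in place of the closing primary-endpoint sentence, state:

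> The primary contrast is the within-subject HAP minus fluoride difference in %MDR at 2 weeks (null hypothesis 2). It answers the comparative objective.

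Replace the declaration sentence in Section B with:

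> The 20% criterion answers null hypothesis 1 only. It is a secondary, within-product result, reported for each product by name, together with the HAP minus fluoride difference and its confidence interval. It will not be described as effectiveness relative to fluoride. A non-significant difference will not be read as equivalence, because no margin is stated.

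Label the before-after tests as secondary. If the sponsor wants to conclude that HAP is no worse than fluoride, that aim and its margin must be specified in advance.

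The wording itself needs no new data or visits. There are two costs. Reaching 20% would no longer support a stand-alone claim against fluoride. The verdict would also rest openly on a contrast with about 64% or 37% two-sided power at 15 subjects, depending on what 12.6 represents, so the power statement should be restated. On the stated difference, 80% two-sided power would take 21 or 40 subjects respectively. If the sponsor keeps 15, the detectable difference at 80% should be given: 9.8 points with SD of differences 12.6, or 13.9 with 17.8.
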